Adequacy of sample size: A sample size calculation was done using the G*Power software. An effect size of 0.27, was estimated (conservatively) based on previous research¹⁰³. With equal numbers of subjects in each group, and alpha = 0.05, to provide 85% power to detect a difference in HTC rates at six months controlling for history of testing, sex, and ethnicity, a sample of 118 per group (total N = 236) is required. Based on adherence rates from our test of the original ***PlayForward*** game we assume 80% retention at 6 months. To account for the 20% dropout we will seek to enroll 296 participants.

Randomization: We will use a stratified randomization procedure¹⁰⁴ to assign participants to one of the study arms. Gender, race/ethnicity, and age will be included in the randomization algorithm because these variables have been found to be important predictors of HTC in adolescents¹⁰³. The stratification would be as follows two gender groups (girl vs. boy), two ethnic groups (Hispanic vs. non-Hispanic), three groups for race (White, African-American, Other) and two groups for age – (14, 15, 16 vs. 17 and 18). A block size of 6 will be used for the stratification process.

Treatment conditions: The research staff will orient the participants to the use of either ***PlayTest!*** or the control videogames. Players in both groups will play through an online tutorial demonstrating the mechanics of the game. Each player will use a dedicated device to access their game on the web and a set of headphones that they will use during each gameplay session. The research staff will oversee all gameplay to ensure that participants are playing and to field any questions. The control videogames (**see below**) will be engaging and fun but will be devoid of relevant content.

Assessments: We will assess participant characteristics (demographic), outcomes, and process measures (Table 1). For outcomes, we will collect data on actual HTC and assess a variety of mediators and moderators among teens (e.g., attitudes, intentions, knowledge). To measure actual testing in our participants, we will work with health care professionals at school clinics located on the premises of our partner sites to determine if students who participated in our study subsequently got tested. This data will be collected based on the protocol of the specific clinic, and the participants’ personal health information will be de-identified (including results) before being

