- ⊕ At the end of each month, the facilitator will check the *Student Identification Form* to identify any students that have utilized the school based health center during that month.
 - If a student has used the health center, then the facilitator will record pertinent information on the *Health Center Participation Form* that is on the password protected excel document for the monthly time period in review.
- ⊕ At the end of each month, the facilitator will meet with a member of the play2PREVENT team for approximately 10-15 minutes. During this brief meeting the SBHC facilitator and the play2PREVENT team member will print the *Health Center Participation Form* for the time period at hand and both parties will sign-off on its completeness. The printed sheet will then be placed in the secured lockbox with the USB drive.
- ⊕ Use the 3000z billing code for participants that come in for a STI/HIV test to protect privacy during insurance billing.

Data analysis

Phase 2: Data analyses general considerations: All statistical analyses will be conducted based on the “intent-to-treat” principle, through the use of either SPSS or SAS statistical packages.

Statistical analyses: **Primary outcome:** The primary outcome will be the proportion of participants who engage in HTC within the six-month study period. Rates of HTC among intervention and control participants at six months will be compared using Fisher’s exact test and a 2-sided test at the 0.05 level. **Secondary outcomes:** To address the secondary outcomes we will use repeated measures ANCOVAs (with Bonferroni corrections to account for multiple statistical tests). The models will include attitudes, perceived barriers, perceived norms, intentions, self-efficacy, and knowledge as dependent variables, with study condition as the independent variable, and sex, ethnicity, and history of testing as covariates. **Mediators and moderators:** Data will be collected on potential mediators and moderators and examined using conventional methods¹¹³. Baseline levels of these mediators and moderators will be used in the models to assess whether these variables affect the primary or secondary outcomes. In addition, because these variables might change over time during participation in the study, they will also be considered as time-varying covariates. **Mediators:** Based on our logic model¹¹² that will guide the development of the proposed intervention, we predict that 1) attitudes, 2) perceived barriers, 3)

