Statistical analyses: **Primary outcome:** Due to COVID-19’s impact on this study’s initial primary outcome of the number of participants that were tested for HIV at the 6 month timepoint, the primary outcome has been modified. Behavioral outcomes are influenced by attitudes and intentions; therefore, we will explore attitudes and intentions in our study, with **attitudes about around HTC** as the new primary outcome. After a thorough review of existing literature, the team decided that the primary outcome would be changed to measuring participant’s attitudes around HTC at 6 months for the full cohort, with intentions and behaviors being assessed as secondary outcomes. **Secondary outcomes:** To address the secondary outcomes we will use repeated measures ANCOVAs (with Bonferroni corrections to account for multiple statistical tests). The models will include attitudes, perceived barriers, perceived norms, intentions, self-efficacy, and knowledge as dependent variables, with study condition as the independent variable, and sex, ethnicity, and history of testing as covariates. **Mediators and moderators:** Data will be collected on potential mediators and moderators and examined using conventional methods¹¹³. Baseline levels of these mediators and moderators will be used in the models to assess whether these variables affect the primary or secondary outcomes. In addition, because these variables might change over time during participation in the study, they will also be considered as time-varying covariates. **Mediators:** Based on our logic model¹² that will guide the development of the proposed intervention, we predict that 1) attitudes, 2) perceived barriers, 3) perceived norms, 4) intentions, 5) self-efficacy, and 6) knowledge will mediate the effects of the intervention on HTC at 6 months. The selection of mediators is based upon the logic model and given the proposed game will have many different components (as our current *PlayForward* game does), and given our experience of including all of these components into a game intervention, this selection of mediators was carefully guided by the process of constructing the logic model. We will use the criteria proposed by Baron and Kenny (1986)¹¹³ to test the relationships among the outcomes and presumed mediators. According to these criteria, four conditions should be met to establish mediation. We outline these conditions using our specific hypothesis that intentions mediate the relationship between the study condition (intervention or control) and HTC as an example. The first condition is that the study condition is directly related to HTC. Second, the intervention condition has a direct effect on the mediator (intentions). Third, intentions have a direct effect on HTC, when the study condition is controlled. Fourth, if intentions mediate the intervention condition-HTC relationship, the direct effect of the study condition on HTC is reduced or eliminated after controlling for intentions. To test the significance of mediation effect, which is called indirect effect, we will calculate Sobel's test¹¹⁴⁻¹¹⁶ for each proposed mediator. Sobel's test determines the significance of the mediation effect by testing the null hypothesis that the indirect effect coefficient is zero (i.e. whether the indirect effect of the independent variable on the dependent variables is significantly different from zero). **Moderators:** Variables that predict the outcome variable (first substance use) differently between treatments will be considered to be moderators using the model outlined by Kraemer et al¹¹⁷. In order to be considered a moderator, the variable must be present prior to randomization and must not be related to the independent variable (*PlayTest!* vs. control games). Pre-randomization variables that interact with the independent variable in predicting the outcome variable (HTC) will be considered moderators of treatment. Variables that predict the outcome variable but do not significantly interact with treatment condition will be classified as nonspecific pre-randomization predictors.

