
Collection and analysis of the in-game data: We will build on systems we have developed to analyze the data collected by the game software or the in-game data⁹⁸, which will serve as the foundation for analytics system built into the game. Briefly, using Player Game State Data (the traditional save/load data so a player can save their progress and pick up later where they left off) and Activity Logging Data (the relevant time-stamped player

actions during gameplay), we will examine the paths taken and decisions made by each player, documenting their exposure to content and the “learning curve” from the in-game data.

All data collected from the assessments will be entered directly into the secure web-based system, OnCore, Yale’s enterprise-wide clinical research management system. OnCore is a fully integrated system development by Forte, which includes three modules: 1) Clinical research management (CRM); 2) Bio-specimen management (BSM); and 3) Patient registry. This project will utilize the CRM module as the electronic data capture system for all case report form data and to support subject tracking. Data will be entered into the OnCore system either by research staff, or with the more sensitive assessments, by the participant themselves. This method limits data entry-associated errors. Before enrolling participants into the intervention, we will conduct a pilot test with two to three participants to assess acceptability and usability of the game, make changes as needed, and confirm data collection procedures.

New proposed plan for analysis approach due to COVID-19

1. Revise power calculations to ensure that a clinically meaningful effect size for the new primary outcome (attitudes around HTC at 6 months in the full cohort) can be detected.
2. Examine **attitudes** around HTC as primary outcome at 6 months in the full cohort.
3. Examine **intentions** to get tested at 6 months in full cohort.
4. Examine **HTC** at 6 months in smaller cohort of students that were able to reach the full 6 months of the study without being impacted by the pandemic (N=135). This study is not powered to detect a difference at this smaller sample size.

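### The 118 per group for 85% power does not follow from the stated inputs, and the COVID-19 plan still uses the resulting 236 to call 3-month HTC powered

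*Combined protocol and SAP*

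**What the plan says.** Section 4 (Research Plan, Phase II Stage 2, Adequacy of sample size) names G*Power and states: "An effect size of 0.27, was estimated (conservatively) based on previous research". With equal groups and alpha 0.05, the aim is "to provide 85% power to detect a difference in HTC rates at six months controlling for history of testing, sex, and ethnicity", and the conclusion is "a sample of 118 per group (total N = 236) is required". Allowing for 80% retention, the target becomes 296.

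The Section 4 data analysis text compares HTC rates by Fisher's "exact test and a 2-sided test at the 0.05 level", with no covariates.

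Section 13 (Statistical Considerations) changes the primary outcome because of COVID-19 to "attitudes around HTC at 6 months for the full cohort, with intentions and behaviors being assessed as secondary outcomes". It names no test for HTC. Its covariate-adjusted models (sex, ethnicity, history of testing) are specified as follows: "The models will include attitudes, perceived barriers, perceived norms, intentions, self-efficacy, and knowledge as dependent variables". HTC is not on that list.

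The COVID-19 plan that closes Section 13 has three relevant items:
- Item 1: "Revise power calculations to ensure that a clinically meaningful effect size for the new primary outcome" (attitudes at six months) can be detected. No result is given.
- Item 4, on six-month HTC with N=135: "This study is not powered to detect a difference at this smaller sample size".
- Item 5, on three-month HTC with N=237: it sets this number against the 236 from Section 4 and describes the study as technically powered at that time point. It calls the halved follow-up a considerable limitation.

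**The concern.** A sample size can be checked only if the effect-size metric and the test are known. A value of 0.27 means very different things as a standardised mean difference, an f, a correlation, a difference in proportions or an odds ratio, and the plan does not say which it is. The calculation also assumes covariate control, whereas the only HTC test ever named is unadjusted and the adjusted models leave HTC out. The power statement therefore matches no HTC analysis in the plan.

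This still matters after the change of primary outcome because item 5 relies on 236. If the figure is too small for the intended effect, a null three-month HTC result could be read as coming from an adequately powered comparison when it did not.

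**Working it through.** **Inputs.** From the sample-size paragraph: effect size 0.27, alpha 0.05, power 0.85, 1:1 allocation, 118 per group, 80% retention. That paragraph does not give sidedness; two-sided is taken from the Fisher test in the Section 4 data analysis text. Control HTC rates of 3-30% are my assumption, because the documents give none.

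**The step that reproduces.** 118 / 0.80 = 147.5, so 148 per arm and 296 in total, as stated.

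**The step that does not.** Let k = (1.960 + 1.036)² = 8.978.

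- *d or h = 0.27:* n per group = 2k / 0.27² = 17.957 / 0.0729 = 246.3, so 247 (248 with the noncentral t). One-sided: 198. Power at 118 per group: Φ(0.27 × √(118/2) − 1.960) = Φ(2.074 − 1.960) = 0.545; noncentral t, 0.542.
- *w = 0.27, 1 df:* total N = k / 0.0729 = 123.2, so 124.
- *f = 0.27, 1 df, 3 covariates (noncentral F):* total N = 126.
- *r = 0.27:* equivalent f = 0.27 / √(1 − 0.0729) = 0.280; total N = 117.
- *Raw difference of 27 points (pooled z):* 33 to 59 per group at control rates of 3-30%.

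| Reading of 0.27 | Needed for 85% power | Power at 236 (118 per group) |
|---|---|---|
| d or h, unadjusted z or t | 247-248 per group | about 54% |
| h, Fisher's exact test, control 3-30% | not computed | 40-49% |
| f (1 df) | 126 total | 98.5% |
| w (1 df) | 124 total | 98.6% |
| r | 117 total | 99.0% |

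Exact Fisher power for h = 0.27 at 118/118 is 0.404, 0.434, 0.465, 0.487 and 0.494 at control rates of 3, 5, 10, 20 and 30%. At N=237 it is about 41-53%, depending on the control rate and on which arm has the extra participant.

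**Does covariate control account for the gap?** For d = 0.27 with three covariates, R² of 0.10, 0.25 or 0.50 needs 223, 186 or 125 per group, and power at 118 per group is 59%, 66% or 83%. Reaching 118 needs R² of about 1 − 118/247 = 0.52. The plan states no R².

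**What unstated inputs reach 118 per group?** An odds ratio of 0.27 at 5.7% vs 18.3% gives 117.9 per group by pooled z. A risk ratio of 0.27 at 4.3% vs 16.1% gives 116.6. A risk ratio of 1.27 at 64.0% vs 81.3% gives 117.7.

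**What 236 can detect.** For an unadjusted z or t test at 85% power: √(2k/118) = √(17.957/118) = 0.39 as a standardised difference; as h, this is for example 10% vs about 24%. Fisher's exact test at h = 0.39 has only about 77-84% power at N=236 or 237, depending on the control rate and the split.

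**The case against.** The strongest reply is that no arithmetic error has been shown. The paragraph cites earlier research for 0.27, and that source may define the metric. Several unstated inputs lead to about 118 per group, and the odds-ratio route lies within a plausible range of HTC rates. Another is d = 0.27 (f = 0.135) averaged over four repeated measures with correlation 0.3: N = 8.978 / (0.135² × 4 / 1.9) = 234 in total. The schedule of assessments has four time points, although the paragraph concerns HTC rates at six months and states no correlation. This reply stands: the figure cannot be reproduced as documented, but it is not proven wrong.

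Three stronger readings are tempting, and the documents do not support them.
- *The trial has only 54% power.* That holds only if 0.27 is d or h without adjustment. Under f, w or r, 236 is about twice what is needed.
- *118 was a total entered as a per-group figure.* The r reading comes close (117), but nothing in the documents settles it.
- *The new primary outcome rests on 236.* It does not: item 1 promises a separate calculation for attitudes, although no result is reported.

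It is also fair to say that HTC is now secondary, that item 4 openly says N=135 is not powered, and that item 5 qualifies its statement. That qualification concerns the shorter follow-up. It does not question the 236.

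**Conclusion.** The point holds. From 0.27, alpha 0.05, equal groups and 85% power, no standard two-arm reading gives 118 per group; an additional, unreported input is needed. Depending on the metric, unadjusted z, t, F or chi-square power at 236 runs from about 54% to about 99%, and Fisher's exact test would put the lower end at 40-49%. The direction of any error is open.

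The calculation corresponds to no named HTC analysis, and item 5's description of three-month HTC as powered therefore cannot be verified. These figures assume two-sided testing at 0.05 and 118 analysed per group; the Fisher ranges also assume control rates of 3-30%. The effect falls on the original design justification and on item 5. For attitudes, the only gap is that the promised calculation is not reported.

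**What to change.** 1. **Adequacy of sample size (Section 4).** Rerun the calculation for the HTC test that will be used. State the effect-size metric, the G*Power procedure, the assumed HTC rate in each arm and any covariate R², and restate the power at 236. If 0.27 is d or h without adjustment, state about 54% (40-49% with Fisher's exact test at assumed control rates of 3-30%).
2. **Section 13.** Name one HTC test, either an adjusted model or Fisher's exact test, and base the HTC power statement on it.
3. **COVID-19 plan, item 5.** Remove both statements that the study is powered for HTC unless the corrected calculation supports them. Give the detectable difference for the chosen test instead: about 0.39 standardised at 85% power for an unadjusted z or t test. If Fisher's exact test is chosen, say that its power at 0.39 is about 77-84% at assumed control rates of 3-30%, depending on the split.
4. **COVID-19 plan, item 1.** Report the result of the promised calculation for six-month attitudes at the number actually analysed.

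The cost is protocol and SAP wording plus one recalculation, with no added participants or visits. The downside is that the stated HTC power may become less favourable and item 5 may lose its powered label.

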 Other: Sign-ups through after-school and school based partners, announcements in health classes, lunch-wave recruitment, open houses & report card nights at the schools, school-wide announcement		

* Requests for medical records should be made through JDAT as described at
<http://medicine.yale.edu/ycci/oncore/availableservices/datarrequests/datarrequests.aspx>

3. Recruitment Procedures:

- Describe how potential subjects will be identified. (See below)
- Describe how potential subjects are contacted. (See below)
- Who is recruiting potential subjects? (See below)

Participation in this study will be strictly voluntary, confidential and non-discriminatory. Participants will be enrolled while they are on-site at one of the participating programs. The study will be advertised in myriad ways including: posters, flyers, letters, sign-ups through afterschool programs, open houses, announcements and

informational table set up during lunch waves, open houses and report card nights. Announcements will also be made during health classes, and mass emails will be sent out to parents/guardians. Participants will be provided with an age-appropriate description of the study and told about what they might expect. In describing the study to the participant, the purpose of the study will be described as “finding out how kids can make choices that are healthier for them”. In describing the study to the guardian/parent, we will indicate that the study will focus on promoting healthy behaviors in adolescence and on providing strategies to assist adolescents in making decisions about the many challenges they face. If a participant or their guardian/parent indicates that they do not wish to participate, there will be no further involvement in the study. We will also obtain agreement from the appropriate administrator at the participating program. The research staff will be recruiting potential subjects.

4. Assessment of Current Health Provider Relationship for HIPAA Consideration:

Does the Investigator or any member of the research team have a direct existing clinical relationship with any potential subject?

Yes, all subjects

Yes, some of the subjects

No

If yes, describe the nature of this relationship. *Write here*

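### With one fixed block size of 6 stated in the protocol, and recruitment and game supervision in the hands of the same staff role, up to 25% of assignments in complete blocks could in principle be known in advance

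*Combined protocol and SAP*

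**What the plan says.** The allocation rule is in the protocol, item 4 (Research Plan), Phase II Stage 2, under Randomization. It begins "We will use a stratified randomization procedure" and ends "A block size of 6 will be used for the stratification process". The stratifying factors are gender (2 levels), Hispanic ethnicity (2), race (3) and age (2, split between 16 and 17). The planned arms are equal, at 148 each.

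Three other places bear on who knows what:

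- Section III, item 3 (Recruitment Procedures): "The research staff will be recruiting potential subjects".
- Item 4, Treatment conditions: research staff introduce each participant to PlayTest! or the control games, and "The research staff will oversee all gameplay to ensure that participants are playing and to field any questions".
- Section IV, item 2: the OnCore database is used to randomise.

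The protocol does not mention varying block sizes, withholding the block size from recruiters, or separating recruiters from session staff. It does not say whether randomisation comes before or after assent and the baseline assessment.

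**The concern.** In a permuted block of known size, the remaining assignments are fixed as soon as one arm has used its places. A person who knows the block size, sees earlier assignments and can place a candidate in a stratum may therefore know the next arm before that candidate joins. Such a person could, knowingly or not, affect who is encouraged, scheduled or kept at the assent step. The arms could then differ at baseline in ways that randomisation is meant to prevent.

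That threat applies to any outcome: HIV testing as well as attitudes. A central system such as OnCore conceals the list, but it does not stop someone deducing the next entry from assignments already seen.

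**Working it through.** The documents give no predictability figure, so there is none to reproduce.

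**Inputs from the protocol:** block size 6; two equal arms, hence 3:3 within a block; 2 × 2 × 3 × 2 = 24 strata; 296 participants, so 296/24 = 12.3 per stratum on average.

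**Assignments known with certainty in a complete block.** There are C(6,3) = 20 equally likely sequences.

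- Positions 1 to 3: never forced.
- Position 4: forced if the first three are alike, 2/20 = 0.10.
- Position 5: forced if one arm is full after four, which means the last two are alike, 8/20 = 0.40.
- Position 6: always forced, 1.00.

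The sum is 0.10 + 0.40 + 1.00 = 1.5 of 6, or 25%. The closed form for block size 2m is a share of 1/(m+1); with m = 3 this is 1/4.

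**Best guess in a complete block.** Guess the arm with fewer assignments so far, and toss a coin when they are level. The chances of being right at positions 1 to 6 are 0.5, 0.6, 0.6, 0.7, 0.7 and 1.0. The sum is 4.1, and 4.1/6 = 68.3%, against 50% with no information.

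**Across the trial.** A stratum of n participants has 1.5 forced assignments per complete block. An unfilled last block adds 0 if it holds up to three participants, 0.1 if four and 0.5 if five. Spreading 296 participants at random over 24 equally likely strata (simulation) gives a mean of 61.4 forced assignments, and 61.4/296 = 20.7%. The documents give no demographic mix. Under one assumed uneven mix the result was again 20.7%. A single stratum would give 24.8%, so 25% is the ceiling.

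**Effect of mixing blocks of 4 and 6**, equally likely, with an observer who knows the two sizes but not their order:

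| | Fixed 6 | Random 4 and 6 |
|---|---|---|
| Known with certainty, 12 per stratum (simulated) | 25% | 6.4% |
| Known with certainty, 36 per stratum (simulated) | 25% | 5.7% |
| Guessing the under-filled arm, complete blocks | 68.3% | 69.3% |
| Largest imbalance within a stratum | 3 | 3 |

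The 69.3% follows from 4 × 0.7083 = 2.833 correct guesses in a block of 4 and 4.1 in a block of 6: (2.833 + 4.1)/10. The guess rate does not fall because the running balance returns to zero at the end of every block, so the guesser need not know where blocks begin or end.

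**The case against.** A reader might infer that recruiters saw every assignment and that a quarter of all assignments were in fact known in advance. The documents do not support that.

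- **Role, not person.** Recruitment and supervision are both given to research staff in general. Nothing says that the same individuals did both.
- **A tally is needed.** Item 6 names several sites, and site is not a stratum. If strata run across sites, a recruiter would need a study-wide count in each of 24 cells. Ethnicity, race category and the age split cannot all be read by sight, and Table 1 places demographics in the baseline assessment.
- **Timing is open.** Under Section III, item 6, consent packets go home and are checked for completeness, and assent is signed at the first meeting. If students with parental consent were randomised in batches, foreknowledge would have little room to act.
- **Allocation may be over.** The COVID-19 analysis plan in item 13 already counts 237 students who reached 3 months and 135 who reached 6 months unaffected by the pandemic.

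All four stand, and they limit the point to an opportunity under stated conditions. They do not remove it: the protocol does not say that batches were used, that recruiters were kept away from sessions, or that the block size was withheld. Staff also keep some discretion over eligibility, scheduling and the assent meeting.

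A second tempting reading is that the point is worse because attitudes are self-reported. That joins two separate problems. Self-report in an open trial invites reporting bias; predictable allocation invites selection bias, whatever the outcome.

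**Conclusion.** The point holds as a low-cost improvement. With fixed blocks of 6, up to 25% of assignments in complete blocks, and about 21% across 296 participants in 24 strata, could in principle be known with certainty before the next participant is enrolled.

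This rests on four assumptions: assignments are made one after another while recruitment continues; someone who recruits knows the block size; that person tracks earlier assignments by stratum; and the candidate's stratum is known before enrolment. The documents neither confirm nor exclude any of them. They give no evidence that selection bias occurred, and fixed permuted blocks contradict nothing else in the plan.

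**What to change.** **If any allocation remains:**

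1. Use randomly varying block sizes, for example 4 and 6, generated in OnCore.
2. Keep the sizes out of the protocol that recruiting staff see.
3. Release each assignment only after assent and the baseline assessment are complete.

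The first step alone is not enough, because it removes most of the certainty but none of the guessing advantage. Withholding the sizes protects what it gains. Late release keeps the assigned arm from influencing assent or baseline answers. Some ability to guess from the running balance will remain. The cost is a system setting and a sentence or two, and the largest imbalance within a stratum does not rise above that of fixed blocks of 6.

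**If allocation is complete, as the COVID-19 plan suggests:** state when randomisation took place relative to assent and baseline, and who knew the block size. Then compare baseline attitudes and intentions between arms by position within block, looking mainly at the later positions, where assignments can be forced. Table 1 collects both measures at baseline, so no new data are needed, provided the allocation order can be recovered from OnCore. With only about 61 forced assignments expected, the check can reveal a gross difference. A clean result would be reassuring but not proof.

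### The 85% power for HTC is stated for a covariate-adjusted comparison, but the only between-arm test named for HTC is an unadjusted Fisher's exact test

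*Combined protocol and SAP*

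**What the plan says.** **Sample size** (item 4, Research Plan, Phase II, Adequacy of sample size). The calculation was done in G*Power; the procedure is not named. "An effect size of 0.27, was estimated (conservatively) based on previous research", with no metric given. "With equal numbers of subjects in each group, and alpha = 0.05", the aim is "to provide 85% power to detect a difference in HTC rates at six months controlling for history of testing, sex, and ethnicity", and "a sample of 118 per group (total N = 236) is required". Enrolment is raised to 296 for 80% retention.

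**Randomization** (same item). "Gender, race/ethnicity, and age will be included in the randomization algorithm", on the ground that these variables predict HTC.

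**HTC analysis** (same item, Data analysis, Primary outcome). "Rates of HTC among intervention and control participants at six months will be compared using Fisher" (the exact version, two-sided, level 0.05). Sex, ethnicity and history of testing appear as covariates only in the repeated measures ANCOVAs for attitudes, perceived barriers, perceived norms, intentions, self-efficacy and knowledge. HTC is not in that list.

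**After COVID-19** (item 13, Statistical Considerations). Attitudes at six months become primary and behaviors become secondary. The COVID-19 analysis plan keeps HTC at six months in 135 participants (item 4, stated not to be powered) and at three months in 237 (item 5). Item 5 says that the study is powered for HTC at 236, though at six months, and calls the shorter follow-up a considerable limitation. No between-arm test for HTC is named there. The mixed-model suggestion that follows concerns dimensional outcomes, which HTC (yes or no) is not.

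**The concern.** A power figure describes a particular test. Here the figure is attached to an adjusted comparison, while the test written down takes no covariates. Three things follow.

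- The 85% cannot be read as the power of the planned HTC test, yet the COVID-19 plan relies on it when it weighs the 237-person analysis.
- The named test ignores the factors that the trial stratifies on because they predict HTC. Ignoring prognostic stratification factors tends to make the comparison conservative, and Fisher's test is conservative already.
- With one analysis implied in the sample size and another in the analysis section, the choice between adjusted and unadjusted HTC results could be made after the data are seen.

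**Working it through.** **1. The texts side by side**

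| Place | HTC comparison |
|---|---|
| Adequacy of sample size | six-month rates, adjusted for testing history, sex, ethnicity |
| Randomization | stratified by gender, ethnicity, race, age group |
| Data analysis, Primary outcome | unadjusted two-sided Fisher's exact test |
| COVID-19 plan, items 4 and 5 | HTC retained, no test named, 236 cited as the powered number |

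**2. The plan's own figure.** Inputs: effect 0.27, alpha 0.05, power 85%, 1:1 allocation. Two-sided is assumed, as in the analysis section. If 0.27 is a standardised difference (Cohen's d or h):

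n per arm = 2 × [(1.960 + 1.036)/0.27]² = 246.3, so 247, not 118.

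Power at 118 per arm = Φ(0.27 × √(118/2) − 1.960) = 55%.

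Other readings also miss. Taking 0.27 as w with 1 df gives 124 in total. Taking it as a risk difference gives 36 to 61 per arm for assumed control rates of 5% to 36.5%. Covariates reach about 118 only if they explain about 52% of the variance (247 × 0.48 ≈ 119), which is not stated. So 118 is not reproduced. The dropout step is: 236/0.80 = 295, against 296 (148 per arm).

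**3. Actual size of Fisher's test.** Full enumeration of two binomials, 118 per arm, nominal 5%, equal rates in both arms (rates assumed):

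| HTC rate | 2% | 5% | 10% | 20% | 30% |
|---|---|---|---|---|---|
| Actual size | 0.7% | 2.1% | 2.8% | 3.5% | 3.7% |

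**4. Illustration of power.** Solve for the h that gives 118 per arm by the unadjusted arcsine test: h = (1.960 + 1.036) × √(2/118) = 0.39. This value is back-solved and is not in the documents. The intervention rate is p₂ = sin²(arcsin √p₁ + h/2). Fisher power at 118 per arm, by enumeration:

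| Control rate (assumed) | p₂ at h=0.39 | Fisher power, h=0.39 | Fisher power, h=0.27 |
|---|---|---|---|
| 2% | 10.9% | 75.0% | 38.2% |
| 5% | 16.7% | 78.5% | 43.4% |
| 10% | 24.4% | 80.3% | 46.5% |
| 20% | 37.5% | 81.6% | 48.7% |
| 30% | 48.9% | 82.3% | 49.4% |

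If 0.27 is w or a risk difference, Fisher power is about 98% or more for control rates of 2% to 40%. None of these readings gives 85%, and they fall on both sides of it.

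**5. Can the data carry an adjusted model?** Expected events = N × (p₁ + p₂)/2, with h=0.39 and control rates of 2% to 10%:

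- N=135: 135 × 0.0645 ≈ 9, to 135 × 0.172 ≈ 23.
- N=237: 237 × 0.0645 ≈ 15, to 237 × 0.172 ≈ 41.

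Arm, testing history, sex, ethnicity and age group make five terms: about 2 to 5 events per term at N=135 and 3 to 8 at N=237. Race in three groups adds two terms, which lowers this to about 1 to 3 and 2 to 6.

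**The case against.** **Currency.** The Fisher sentence belongs to the pre-COVID primary analysis. Item 13 makes attitudes primary and does not repeat Fisher's test. The COVID-19 plan calls for new power calculations for attitudes, says that HTC at N=135 is not powered, and qualifies the three-month analysis. This stands, and it lowers the stakes. It does not close the point: the Fisher sentence is not marked as superseded, no other between-arm HTC test is named, and item 5 of the COVID-19 plan still leans on 236.

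**Validity.** Fisher's test keeps its level; its actual size is below 5% throughout the table. This stands. A reader might infer a false-positive risk, and there is none. The cost is conservatism.

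**Magnitude.** A reader might take the drop from 85% to 75%–82% as the price of omitting covariates. It is not: both tests in that comparison are unadjusted, and the documents give no covariate R² or HTC rates from which to work out that price. A reader might also infer that HTC is necessarily underpowered. The documents do not support that, because the direction depends on what 0.27 measures.

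**Other HTC models.** It would overstate the case to say that no HTC modelling is planned. The mediation steps and moderator interactions model HTC on study condition. They name no link function and no adjusted between-arm estimate, so they do not fill the gap.

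**Feasibility.** A full logistic model is fragile with so few events, and excluding anyone tested in the past year narrows the testing-history covariate. This stands and shapes the fix.

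**Conclusion.** The mismatch is on the face of the document and remains live: adjusted power, unadjusted test, and a later section that still relies on the power figure. It concerns what is now a secondary outcome, so it should be corrected but is not a defect in the current primary analysis.

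Its size cannot be determined. The 75% to 82% rests on an assumed h of 0.39 and assumed control rates of 2% to 30%; the sizes of 0.7% to 3.7% rest on the same range of assumed rates. That 118 per group does not follow from 0.27 is a separate and larger problem. Changing the test does not repair it; stating the metric and the rates is necessary in any case.

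**What to change.** **In Data analysis (item 4), Statistical Considerations (item 13) and the COVID-19 plan:**

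- Compare HTC between arms with a covariate-adjusted analysis that uses testing history, sex and ethnicity (the covariates in the sample-size statement) plus age group. Add race if events allow, by a rule fixed in advance.
- Report a standardised risk difference with a 95% confidence interval.
- Pre-state a sparse-data method, for example penalised logistic regression, and the event count at which it applies.
- Keep Fisher's exact test as a sensitivity analysis.

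**In Adequacy of sample size and COVID-19 plan item 5:** restate the power for the test actually used, giving the metric of 0.27, the assumed HTC rate in each arm and any R² credited to covariates.

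**Cost:** wording, plus one power calculation. No new data are needed: gender, age and HTC history are in the baseline assessment, and race and ethnicity are needed to randomise. The downside is that the adjusted model may be unstable with few events, which the pre-stated sparse-data method is there to cover.
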